Exclusion criteria: Participants will be excluded if they have any neurological condition, such as TBI, history of blast exposure, stroke, brain tumors, epilepsy etc. They will also be excluded if MRI scanning is contra-indicated, e.g. due to an implanted device such as a pacemaker, or foreign bodies of ferromagnetic nature. Cognitive screening will be performed using the Repeatable Battery for Assessment of Neuropsychological Status (RBANS, Randolph, 1998) and those with cognitive impairment will be excluded based on a score of 1.5 SD below the mean for the Verbal Memory Index. We will test subjects' hearing using a validated screening questionnaire (Screening Version of the Hearing Handicap Inventory for the Elderly, HHIE-S, Wentry & Weinstein, 1983, Lichtenstein et al., 1988) followed by assessment of audiometric pure tone (0.5, 1.0, 2.0, 4.0 KHz) hearing thresholds in the CVNR sound booth. Those with more than mild hearing loss (HHIE score >8 or audiometric thresholds >40dB) will be excluded (Wentry & Weinstein, 1983; Wilson, 2009), given that we are relying on audio cues. CVNR investigator [name] has considerable experience with audiometric testing and will train the research assistant working on this project to perform testing (see letter of support). We will also exclude visually impaired veterans who are dependent on a wheelchair or scooter for mobility, as they will not be able to take part in the real-world task. Although visual disturbances following TBI are clinically important, they are heterogeneous and blindness is uncommon after TBI; thus, rehabilitation of visual problems after TBI will likely require approaches differing from that in the present proposal. Given the likelihood that many veterans with visual loss will be over the age of 65, it is recognized that they may have a number of comorbid conditions, including diabetes, hypertension and cardiovascular disease. These will not, however, be automatic exclusion criteria, although such conditions will alert us to the possibility of confounding conditions such as white matter disease – if their MRI scans obtained for clinical reasons or

during the course of this research show more than minimal white matter disease, they will be excluded.

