Study flow (Fig. 2): Participants will take part in an initial session of behavioral testing and fMRI scanning, and another similar session after training. In the intervening 3 weeks, they will attend 12 training sessions of one hour each, comprising either the experimental or control intervention. These sessions will take place each weekday from Monday-Thursday, beginning the Monday after the initial session, and will be conducted via the internet with the participant at home, using CVNR-issued iPads. The Friday of each week will be used for repeat testing on the spatial imagery task to assess the extent of improvement as a result of the preceding four days' training. This design allows 12 hours of training over 3 weeks, comparable to that used in prior studies of spatial cognitive training (Wright et al., 2008; Terlecki et al., 2008). In addition, it allows us to

assess weekly improvement, thus providing crucial data for design of a larger study in the future. Importantly, CVNR investigators have experience using iPads with their built-in accessibility for those with visual impairments, and experience with this kind of telehealth application. They have found that even older, technologically naïve caregivers (mean age 78±4.1) can learn to use novel technologies such as the iPad; with a high degree of reported satisfaction (Griffiths et al., 2016). Specifically, Co-investigator [name] has expertise in use of telehealth technology with visually impaired participants in a VA project where he assessed the accessibility of smart phones including the iPhone and in an NIH SBIR project in which the accessible and award-winning MoneyReader app was developed for the iPhone and iPad. The training sessions will employ a haptic grid overlay on the iPad screen during training, and

software will be developed to enable remote communications and viewing of the subject's movements and finger position on the screen of the iPad.

Spatial imagery task: The imagined grid used for the spatial imagery task as well as for spatial cognitive training will be a 5x5 grid using the numbers 1-25, with 1-5 on the first row from left to right, 6-10 on the second row from left to right, and so on (**Fig. 3**). Participants will first

Initial positions: white numbers. Arrows: shortest paths from initial to final position, intersecting with mentally traced sequence (right) or not (left).

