Interventions: The experimental intervention (spatial cognitive training) will comprise repeated practice of the spatial imagery task with feedback after each trial. Training will be conducted in the participant's home using an iPad issued to the subject at the initial visit, and live video communication with a research assistant at the CVNR over the internet. The iPad will be programmed to allow administration of the spatial imagery task. As in the version of the spatial imagery task administered at initial and final testing, audio cues will trigger mental navigation through the grid using audio cues, with haptic reinforcement via tactile overlays for the screen (to permit sensory facilitation of learning). Following each sequence traced, subjects will be asked whether the shortest path back to the origin intersects with the sequence traced or not. If the answer is incorrect, the research assistant will show the correct path for the subject to trace mentally and haptically. In the control intervention, subjects will be taught letter correspondences to the numbers (e.g. 1->A, 2->B and so on until 25->Y), using a similar setup and procedure as in the experimental intervention.

Behavioral measures: The following behavioral measures will be collected before and again after training with the experimental and control interventions: (1) Performance (directional accuracy and response time [RT]) on the spatial imagery task will be acquired during fMRI scanning. (2) In addition, pointing accuracy will be measured on the real-world path integration task in the MSL, in terms of the angular difference between the target of pointing and the actual initial position. (3) We will also measure performance, with standardized neuropsychological tests, at baseline as well as at post-training, on (a) spatial memory using a haptic version (produced in the [name] lab using textured blocks) of the Corsi block test (Kessels et al., 2000), (b) the verbal memory tests of immediate and delayed memory from the RBANS (Randolph, 1998) and (c) verbal working memory tested by the Forward and Backwards Verbal Digit Span test from the Wechsler Adult Intelligence Scale (Wechsler, 2008). A research assistant will be trained by the PI and [name], Co-investigator on this project, to administer all the tests, as well as the training procedures.

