Imaging measures: The following imaging analyses will be conducted on data acquired before and again after training with the experimental and control interventions: (1) A univariate contrast between the experimental and control conditions will provide insight into the brain regions responsible, and the **magnitudes of activation** in key brain regions will be assessed. (2) Multivariate pattern analyses (Kriegeskorte, 2008) will be used to assess **representational similarity in the neural representations of paths**. (3) Further, we will use **multivariate effective connectivity analyses**, which our group has considerable experience with (Hampstead et al., 2011; [name] et al., 2013; Lacey et al., 2014), to examine patterns of connectivity during task performance. (4) In addition, we will assess **resting-state connectivity** patterns using the activated regions as seeds. (5) Finally, we will also acquire diffusion tensor imaging (DTI) scans to assess **structural connectivity**.

Imaging design: The same spatial imagery task as outlined above will be used during fMRI scanning in an event-related design, with pseudorandomly interleaved trials of a control task requiring judgment of whether the majority of numbers in the audio sequence are odd or not. On each trial, the stimulus presentation will occupy 4s or 5s, depending on whether the sequence comprises 4 or 5 steps in the grid. These two trial durations will be interleaved in pseudorandom order, as will experimental and control trials. Participants will be verbally instructed to make their keypress response following the last auditory cue. A blank interval varying from 4-8s will intervene between trials: this jitter allows for better estimation of the signal on each trial than designs with a fixed inter-trial interval. Each run of trials will also include six pseudorandomly interspersed 10s blank periods for estimation of baseline signal. Functional runs will last 9min 20s, comprising a total of 40 trials (20 experimental and 20 control). 4 such runs will be conducted.

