Imaging parameters: Imaging will be conducted on the Siemens Magnetom Prisma 3T MR scanner in the Biomedical Imaging Technology Center at Emory University Hospital. **Structural** scans comprise a T1- and T2-weighted (T1w, T2w) scan. The T1w scan uses a 3D magnetization-prepared rapid gradient echo (MPRAGE) sequence (repetition time (TR)=2400 ms; echo time (TE)=2.14 ms; inversion time=1000 ms; flip angle (FA)=8°; bandwidth (BW)=210 Hz/Px). The T2w scan uses a 3D T2-SPACE sequence (TR=3200 ms; TE=565 ms; variable FA; BW=744 Hz/Px). For both sequences, field of view (FOV)=224×224 mm; 0.7mm isotropic voxels; iPAT factor=2. **Functional** scans, which measure the blood oxygenation level-dependent (BOLD) signal, are acquired using gradient-echo echoplanar imaging (EPI) sequences (TR=1000 ms; TE=25 ms; FA=52°; field of view (FOV)=208×180 mm; 72 slices; 2.0 mm isotropic voxels; multi-band factor (MBF)=8; echo spacing (ES)=0.58 ms; BW=2290 Hz/Px). **DTI scans** use a spin-echo EPI sequence (TR=5520 ms; TE=89.5 ms; FA=78°; refocusing FA=160°; FOV=210×180 mm; 111 slices with 1.25 mm isotropic voxels; MBF=3; ES=0.78 ms; BW=1488 Hz/Px; phase partial Fourier 6/8).

PROTECTION OF HUMAN SUBJECTS

Sources of materials

No specimens will be obtained. Research data consist of performance data acquired during behavioral and scanning studies and MR imaging data, all obtained solely for the purpose of the research outlined. Upon enrollment, participants will be assigned code numbers and all data acquisition and analysis will be performed using these de-identified code numbers, with the keys linking to individual identifiers being secured along with any private health information and individually identifiable information on password-protected computers and in locked file cabinets within locked laboratories.

RISKS TO HUMAN SUBJECTS

Potential risks

MRI scanning

A risk of MRI scanning, which is in very wide general use, is the possibility of damage created by movement of a ferromagnetic metallic implant or foreign body such as a pacemaker or aneurysm clip. As is routine, any subject with such an implant or foreign body will be excluded by meticulous screening of subjects by an experienced MRI technologist. There is also a small risk of thermally induced burns caused by electromagnetic loops; care will be taken by an experienced MRI technologist running the scanner to exclude such loops. With these precautions, MRI scanning is safe.

Behavioral

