All the structural MRI scans will be initially reviewed by the MRI technician and if needed, will consult with [name], a neurologist with experience in reviewing clinical neuroimages. In the event incidental findings are noted that might be abnormal, the images will be further reviewed by a clinical neuroradiologist. Any verified abnormalities will be communicated to the participant by the PI or Co-I, and an appropriate course of action will be recommended. Depending on the finding, this recommendation may vary from no action (e.g. in case of a small arachnoid cyst) to obtaining a full clinical series and neurological or neurosurgical consultation. This procedure will be disclosed to participants on the informed consent forms, along with a reminder that the scans to be obtained on the project are not intended for clinical diagnosis.

POTENTIAL BENEFITS

Participants randomized to the experimental intervention may experience some improvement in their spatial skills, which may help them navigate their environment better. Those randomized to the control intervention are not expected to show such gains, but will be offered the opportunity to undergo the experimental intervention after they complete participation. Participants will experience the satisfaction of contributing to scientific knowledge and ultimately to better methods of rehabilitation.

IMPORTANCE OF KNOWLEDGE TO BE GAINED

Vision loss is a highly significant problem in the veteran population, and the long-term goal of this research is the application of current neuroscientific insights to design novel rehabilitative approaches for visual rehabilitation of veterans with vision loss. We propose that spatial cognitive training would be a very useful training intervention for rehabilitation of veterans with low vision and blindness, to complement and enhance existing O&M training programs.

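### The white matter exclusion has no visit limit, grading criterion or specified masking, so as worded it allows removal of participants after randomisation and possibly after training

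*Combined protocol and SAP*

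**What the plan says.** The Exclusion criteria note that many participants will be over 65 with vascular comorbidities. These are not automatic exclusions, but "such conditions will alert us to the possibility of confounding conditions such as white matter disease". The operative rule follows: if scans obtained for clinical reasons or "during the course of this research show more than minimal white matter disease, they will be excluded". It names no visit, grading scale, reader or deadline.

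On when research scans happen, Study flow says: "Participants will take part in an initial session of behavioral testing and fMRI scanning, and another similar session after training". Training starts soon after the first of these, "beginning the Monday after the initial session". Imaging measures adds: "The following imaging analyses will be conducted on data acquired before and again after training with the experimental and control interventions"; that list includes diffusion tensor imaging. Imaging parameters says the structural "scans comprise a T1- and T2-weighted (T1w, T2w) scan", without giving the visit.

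On who looks at the scans, the only text is under Incidental findings: "All the structural MRI scans will be initially reviewed by the MRI technician", with a neurologist consulted if needed. That section deals with clinical follow-up of abnormalities, not eligibility, and does not mention masking.

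The Participants section has 60 people randomised into two groups by the statistician. It does not say when this happens relative to the first scan. The Analyses section specifies a group by session repeated-measures ANOVA for each behavioural measure. It defines no analysis set and does not say what happens to the data of someone excluded after randomisation.

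**The concern.** The rule expressly reaches scans made during the study, and the only research scanning sessions described are the initial one and the one after training. Nothing confines it to a scan read before assignment. By the final session the study team can know how a participant has done. Imagery-task performance is recorded in the scanner (Behavioral measures), and the Friday retests track progress each week (Study flow).

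The criterion also leaves room for judgement. The same section gives numeric limits for hearing and for cognition, but none for white matter disease. A borderline scan could be called either way.

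Two things are at stake. The first is the randomised comparison itself. The Participants section relies on randomisation to balance comorbid conditions, which holds only if those randomised stay in the analysis. The second is the effect size. The end of Preliminary Studies says the project should supply one for sizing a larger trial, so a distorted estimate would carry into the next study.

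**Working it through.** **1. Does the wording reach past randomisation?**
- Scans covered: clinical scans, or any scan during the research (Exclusion criteria).
- Research scanning: one session before training and a similar one after (Study flow). No separate screening scan is described.
- Randomisation: timing relative to the first scan not stated (Participants).

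On the literal wording, the post-training session is covered. If randomisation precedes the initial session, a removal based on the first scan is also post-randomisation.

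**2. The plan's own power figure.** The Participants section states power 0.81 for 60 participants, effect size 0.9, alpha 0.05. With two sessions, the group by session interaction is equivalent to a two-sample t-test on change scores. Assume 1:1 allocation, a two-sided test, and 0.9 as a standardised difference in change. The normal approximation is power = Φ(d√(n/2) − 1.96), with n per arm.
- n = 30: Φ(0.9 × √15 − 1.96) = Φ(1.526) = 0.936; exact t, 0.929.
- n = 20: Φ(0.9 × √10 − 1.96) = Φ(0.886) = 0.812; exact t, 0.792.

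The stated 0.81 is not reproduced at 60. It is reproduced at 40, which is what the Timeline implies (20 months × 2). That is a separate inconsistency; here it means that both bases should be shown.

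**3. Removal unrelated to arm and outcome.** There is no bias, only lost numbers. The documents give no exclusion rate, so equal losses of 5% to 30% in both arms are assumed (exact t):

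| Loss | Power from 60 | Power from 40 |
|---|---|---|
| 0% | 0.929 | 0.792 |
| 5% | 0.916 | 0.770 |
| 10% | 0.901 | 0.746 |
| 20% | 0.863 | 0.693 |
| 30% | 0.812 | 0.630 |

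**4. Removal related to arm and change (illustration only).** Suppose a share q is removed from one arm only, on a reading that correlates r with change (normal scores, less improvement going with removal). The mean of those retained shifts by r × φ(z)/(1 − q), in SD of change, where z is the upper-q normal quantile. For q = 0.10 (3 of 30), φ(1.2816)/0.90 = 0.1755/0.90 = 0.195. For q = 0.05, 0.1031/0.95 = 0.109. For q = 0.20, 0.2800/0.80 = 0.350.

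| q | r = 1 (lowest scorers) | r = 0.5 | r = 0.2 | r = 0 |
|---|---|---|---|---|
| 0.05 | 0.109 | 0.054 | 0.022 | 0 |
| 0.10 | 0.195 | 0.098 | 0.039 | 0 |
| 0.20 | 0.350 | 0.175 | 0.070 | 0 |

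Removal from the experimental arm inflates the estimated effect; removal from the control arm shrinks it.

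**5. Carry-over to the larger trial.** Required sample size scales with 1/d². If a true 0.9 were estimated as 0.9 + 0.10 = 1.00, the next trial would have (0.9/1.00)² = 0.81 of the needed size, or 19% too few. At 0.9 + 0.195 = 1.095 the ratio is (0.9/1.095)² = 0.68, or 32% too few.

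**The case against.** The strongest reply is that this is an eligibility criterion. It sits under Exclusion criteria, and its contrast is between clinical and research scans, not between visits. The post-training scan is never named, and the visit for the T1- and T2-weighted scans is not stated. The two sessions are about three weeks apart, so disease beyond the threshold should normally be visible on the first scan. The intended use may well be the initial scan only. This stands as a reading of intent, but that intent is not written down. It also does not settle the matter, because randomisation may precede the initial scan.

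A second reply concerns size. The planned test is on change, and a stable trait that lowers performance at both sessions largely cancels. A rule applied alike in both arms would not by itself create a difference between them. This stands too: the shifts in step 4 require removals in one arm that are related to change.

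Two stronger readings are tempting and should not be adopted. A reader might infer that the scan reading is unmasked. The documents are silent: they name no reader for this decision and specify no masking, which is a gap and not a statement that the reader knows the arm. A reader might also infer that allocation is known at the first scan, because training is done "using an iPad issued to the subject at the initial visit". That does not follow. Both arms train on centre-issued iPads with a similar setup, so issuing one neither reveals the arm nor dates the randomisation.

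**Conclusion.** The point holds as a matter of wording. The rule is open-ended in time, has no criterion for its threshold, specifies no masking, and is not backed by an analysis set that retains everyone randomised. Followed as written, it permits removal after randomisation and possibly after training. The documents do not show that such removals will occur, or that they would be selective.

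The main risk is bias rather than power, and its size cannot be computed from the documents. On assumed figures for one arm at 10% removal, the shift runs from zero (unrelated to arm and outcome), through about 0.10 SD (correlation 0.5 with change), to about 0.19 SD (the lowest change scores removed). The last is roughly a fifth of the planning effect of 0.9 (0.195/0.9 = 0.22). This is a worthwhile, inexpensive correction, not a flaw that invalidates the design.

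**What to change.** Amend the Exclusion criteria and Analyses sections as follows.
- Apply the white matter exclusion only to clinical scans and the initial research scan.
- State in advance the grading criterion that defines the threshold, and who applies it.
- Complete and record the reading before the assignment is released. The reader then cannot know the arm, with no separate masking procedure needed.
- Analyse every randomised participant in the assigned group.
- Record white matter findings from later scans and use them only in a sensitivity analysis.

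The cost is mainly wording. The practical burden is that the initial scan must be read and the assignment released before training starts on the following Monday, which may be only days later. A few participants whose white matter disease is noticed late will stay in the primary analysis. That adds some heterogeneity, but keeps the randomised comparison intact.

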In order to lay the groundwork for a future Merit Review proposal investigating the utility of spatial cognitive training in visual rehabilitation, the currently proposed SPiRE project seeks to establish the feasibility of such training in visually impaired participants over a telehealth interface, to obtain data on the effect size of the training relative to a control intervention to provide a basis for sample size estimation in a larger clinical trial, and to examine the relevant neural mechanisms so as to suggest possible synergistic interventions that would enhance the effects of spatial cognitive training. Importantly, the proposed work will examine the real-world generalizability of the training effects using physical walking spaces to assure relevance to rehabilitation.

Research Design and Methods

PARTICIPANTS

We will recruit 60 blind participants, randomized by our CVNR statistician into two groups. One group will undergo the experimental intervention (spatial cognitive training) and the other will undergo a control intervention involving letter-number matching. The participants will include women and minorities in proportion to the demographics of the veteran population attending the Atlanta VA. Working with our statistician, we calculated that this sample size has a power of 0.81 to detect an effect size of 0.9 with $\alpha=0.05$ and $\beta=0.19$. The randomization process should result in a balance between the intervention and control groups with respect to a range of variables, including age, sex, age of onset of visual loss, duration of visual loss and of loss of light perception, and comorbid conditions; any residual differences will be accounted for as covariates in statistical analyses.

Since the participants are blind or have low vision, they will need transportation to the CVNR, which will be provided via a contractual arrangement in place with the CVNR. Subjects will be compensated for their time at a flat rate of \$150 for participation in all sessions of the study. If they drop out or are otherwise unable to complete the study, compensation will be prorated for the number of sessions they participate in.

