Specific Aim I will test the hypothesis that spatial cognitive training of blind veterans on a spatial imagery task leads to improvements in **(a)** performance on the trained spatial imagery task and **(b)** real-world navigational ability, relative to a control intervention. If the hypothesis is supported, this would be a simple method of spatial cognitive training with real-world benefits that could eventually be administered via telemedicine. **Specific Aim II** will use functional magnetic resonance imaging (fMRI) to assess the neural changes associated with spatial cognitive training. The hypothesis is that those in the spatial cognitive training group will show enhanced activation in brain regions mediating spatial processing, such as the hippocampus and parietal cortex, as well as more differentiated neural representations of imagined paths. The benefit of pinpointing the neural loci of change is the identification of potential targets for application of converging rehabilitation approaches, e.g. transcranial magnetic or electrical stimulation over parietal regions; enhancing hippocampal neurogenesis through aerobic exercise. If the present proposal is successful, subsequent research will be needed to determine how best to incorporate such training into programs that complement current O&M training.

ANALYSES

In **Specific Aim I**, each behavioral measure will be subjected to a repeated-measures ANOVA with a between-subjects factor of group (experimental, control) and a within-subjects factor of session (pre-training, post-training); the null hypothesis will be rejected in case the interaction is significant at $\alpha=0.05$. If the interaction is non-significant, the Bayes factor will be calculated to ascertain whether this (less likely) supports the null hypothesis or (more likely) reflects insufficient power (Dienes, 2014); in the latter case, the data can be used to estimate the sample size for a subsequent study. In **Specific Aim II**, the imaging measures acquired (except

for DTI) will be subjected to similar two-factor ANOVAs as in Aim I, and statistical interpretations will follow similar lines.

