We predict that spatial cognitive training, but not the control intervention, will lead to improvements in performance on the spatial imagery task, its analog in the MSL, and the various functional neuroimaging measures. There may be transfer of spatial learning to the spatial memory task, but we do not expect transfer to the verbal memory and working memory measures, indicating the spatial specificity of training. We hypothesize that spatial cognitive training, but not training on the control intervention, will lead to increases in activation in cortex along the IPS and in the FEFs as well as in the hippocampus, increased strength of connectivity between these regions in the task and resting states, and also to more differentiated representations between different paths (i.e. their representations will show higher dissimilarity). The behavioral and neuroimaging measures obtained at baseline, including DTI measures of structural connectivity between the activated brain regions, will be tested as regressors to establish whether they predict changes in the repeated measures. This will be useful to examine the impact of individual differences in pre-training spatial and verbal abilities on the effects of training, and in the design of further studies aimed at targeting interventions tuned to individual performance in specific domains.

TIMELINE

First 2 months: Set up tasks and initiate recruitment

Next 20 months: Test and train 2 subjects per month, one in each group

Last 2 months: Analyze data and prepare publications

FUTURE DIRECTIONS

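### The trained imagery task is tested weekly, but its planned analysis uses only two sessions: the Friday scores get no between-group estimate, and the effect is exposed to unequal, progress-related dropout

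*Combined protocol and SAP*

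**What the plan says.** Under PROCEDURES, Study flow, participants have an initial session of behavioural testing and scanning, 12 training sessions over three weeks, and a similar session afterwards. In between, "The Friday of each week will be used for repeat testing on the spatial imagery task to assess the extent of improvement". The section says that the design makes it possible to "assess weekly improvement, thus providing crucial data for design of a larger study in the future".

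Under ANALYSES, every Aim I behavioural measure goes into a repeated-measures ANOVA with a group factor and "a within-subjects factor of session (pre-training, post-training"; the test is the interaction at 0.05. No method is given for the Friday scores.

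Dropout appears in the PARTICIPANTS section only as a payment matter ("If they drop out or are otherwise unable to complete the study"). The exclusion criteria also allow removal when a scan taken during the research shows more than minimal white matter disease. No analysis set, dropout rate or missing-data rule is stated.

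**The concern.** Two things are at stake.

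- **Weekly course of training.** One aim of the project is an effect size against control for planning a larger trial. With no between-group contrast specified for the Fridays, week-by-week gains could be read within each group, where training is mixed with practice from repeating the test.
- **Main effect on the trained task.** A two-session ANOVA needs both scores. Someone who attends two Fridays and then leaves contributes nothing, although those scores show how that person was progressing. The arms do different work (spatial path integration with corrective feedback, against letter-number matching), so different reasons for leaving are plausible, though not documented.

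**Working it through.** **1. The plan's own figure.** With two sessions, the group-by-session interaction is a two-sample t-test on change scores. The plan says "We will recruit 60 blind participants, randomized by our CVNR statistician into two groups" and that this sample "has a power of 0.81 to detect an effect size of 0.9". Read 0.9 as a standardised difference in change, two-sided 0.05, equal arms; normal power is Φ(d√(n/2) − 1.96).

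- n = 30 per arm: 0.9 × √15 = 3.486; Φ(1.526) = 0.936 (exact t: 0.929).
- n = 20 per arm: 0.9 × √10 = 2.846; Φ(0.886) = 0.812 (exact t: 0.792).

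The stated 0.81 fits 20 per arm, not 30. The timeline also implies 40 participants ("Next 20 months: Test and train 2 subjects per month, one in each group": 20 × 2 = 40). With 60 enrolled and 30% lost (21 per arm), exact t gives 0.812, but no loss rate is stated, so the figure cannot be read as an allowance for dropout. That discrepancy is a separate matter; the checks below use 30 per arm.

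**2. Number of measurements.** Initial + three Fridays + final = 5, or 4 if the third Friday is the final session. The text does not settle this and the study-flow figure was not available. The calculations use five.

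**3. Completer bias in closed form.** Assumptions not in the documents: outcome SD 1; correlation 0.5 between any two visits; a fraction p of the trained arm leaves after the second Friday, lowest first on observed change so far plus noise of SD 0.5; no control leaves.

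- Variance of the dropout score: 2(1 − 0.5) + 0.25 = 1.25.
- SD of pre-to-post change: √(2(1 − 0.5)) = 1.
- Covariance of the two: 1 − 0.5 = 0.5.
- Correlation: 0.5/√1.25 = 0.447.
- Bias in SDs of change: 0.447 × φ(z_p)/(1 − p), with z_p the p-quantile of the standard normal.

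| p | φ(z_p)/(1 − p) | Bias | As % of 0.9 |
|---|---|---|---|
| 10% | 0.195 | 0.087 | 9.7% |
| 20% | 0.350 | 0.157 | 17.4% |
| 30% | 0.497 | 0.222 | 24.7% |

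**4. Simulation.** 30 per arm, linear gain over three weeks, effect 0.9 SD of change, 400 replicates per setting. Ranges cover three correlation patterns: constant 0.5, constant 0.7, and first-order autoregressive 0.85. The mixed model has group-by-visit means and unstructured covariance.

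| Dropout | ANOVA estimate / truth | Mixed model / truth | ANOVA type I error | Mixed model type I error |
|---|---|---|---|---|
| None | 1.01 | 1.01 (identical) | 0.05-0.06 | same |
| 20%, poor progressors, both arms | 0.98-1.00 | 0.98-1.01 | 0.06-0.09 | 0.06-0.07 |
| 10%, trained arm only | 1.07-1.10 | 0.98-0.99 | 0.06-0.08 | 0.05-0.06 |
| 20%, trained arm only | 1.14-1.18 | 0.98-1.00 | 0.10-0.12 | 0.06-0.07 |
| 30%, trained arm only | 1.22-1.32 | 0.98-1.03 | 0.11-0.18 | 0.05-0.06 |

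Simulation error is about 1 to 2 percentage points. For constant correlation 0.5 the simulated overstatements (8.4%, 16.8%, 22.3%) agree with step 3 within that error. With 20% random loss in both arms, neither analysis is biased; power is 0.86-0.87 for the ANOVA and 0.88-0.91 for the mixed model.

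**5. A less one-sided case.** True effect 0.5 SD, 22% progress-related loss in the trained arm, 10% random loss in controls: completers 0.63, mixed model 0.51, same data without dropout 0.51. With the same dropout rule in both arms, all three were 0.50, and the standard errors were 0.242 (mixed) and 0.246 (ANOVA).

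**6. Does the Friday setting matter?** Pre and post scores come from the scanner; the Friday setting and scoring are not stated. Multiplying all Friday scores by 37 and adding 10 left the mixed-model post contrast unchanged to 2 × 10⁻⁷, because visit-specific means and unstructured covariance absorb any linear change of scale. Weakening the Friday-scanner correlations by 15% and 30%, under a stricter dropout rule and a true effect of 0.5, gave completers 0.75 and 0.73 and the mixed model 0.50 both times.

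**7. Where the mixed model falls short.** When dropout depended on the unobserved post-training change, full data gave 0.49, completers 0.83 and the mixed model 0.68. The excess falls from 0.83 − 0.49 = 0.34 to 0.68 − 0.49 = 0.19, so more than half remains.

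**The case against.** A reader might infer that the plan discards non-completers by rule. It does not say so: that follows from the ANOVA as ordinarily run, and the plan is silent on the analysis set. Nor are the Friday tests wasted. They have a stated purpose, both arms take them, and a between-group comparison is available, though none is written down. With complete data they add nothing to the pre-to-post contrast.

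The strongest objection is that the bias needs a particular condition. Poor progress driving people out is not enough; it must do so more in one arm than in the other. The documents give no dropout rate or pattern. In the case in step 5 the excess of about 0.12 is roughly half a standard error. Steps 4 and 5 also make dropout depend on observed scores, the condition under which a likelihood model is expected to recover the truth. Finally, this is a proof-of-concept study, and the change reaches one outcome only.

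All of this limits the size and reach of the point. It does not remove the mismatch between weekly testing and a two-session model, nor the absence of any protection if loss is unequal.

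**Conclusion.** The point holds in a limited form. Imagery performance is measured four or five times, the only specified model uses two of those measurements, and the Friday data have no specified between-group estimate. The planned test is in effect a completers' comparison. Under assumed progress-related loss from the trained arm only, it overstates the effect by roughly 7-10% at 10% loss, rising to 22-32% at 30%, with type I error up to 0.18. These figures are illustrative and rest on the assumed effect, correlations and dropout rule. Equal loss in both arms gives no bias, and no loss gives the same answer from both analyses.

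The documents do not support saying that the planned estimate is biased, only that it is unprotected against a plausible pattern of loss. Nor would a mixed model remove every dropout bias (step 7). The change is worth making because it costs little and loses nothing when data are complete.

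**What to change.** For spatial imagery performance only, replace the two-session ANOVA with a likelihood-based linear mixed model:

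- all randomised participants, in their assigned group, with any score;
- categorical visit (pre, each Friday, post), group, group-by-visit, and unstructured covariance;
- the group difference in pre-to-post change as the test;
- the group contrasts at each Friday reported as the weekly effects.

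State whether the third Friday is separate from the final session, and where and how the Friday tests are scored. Keep the Friday scores in the joint model even if their setting or scale differs from the scanner's. Modelling them separately would leave the post-training contrast as a completers' analysis.

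State the missing-at-random assumption and add a sensitivity analysis for dropout that depends on unobserved scores, for example by shifting the imputed post-training scores of trained-arm dropouts downwards over a stated range.

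The cost is analysis wording and slightly more analysis work, with no new visits or data. Real-world pointing and the neuropsychological tests are measured only before and after training. This change does not help them, and they still need a stated rule for missing post-training scores.
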